Traditional Home Health Physical Therapy Versus a Smartphone App for Patients Recovering from Total Knee Arthroplasty During the Home-bound Portion of Recovery: Study Protocol for a Randomized Controlled Trial

by [name] [name], PT, DPT

Study Design

Prospective randomized controlled trial comparing traditional home health care physical therapy to physical therapy provided via a smartphone app for patients recovering from total knee arthroplasty (TKA)

Background

As of 2013, it was estimated that 4.0 million individuals in the U.S. were living with a TKA, representing 4.2% of the population fifty years of age or older (8). As of 2010, there were 81,489,445 people aged 45 to 64 in the U.S. (4), with a rate of 39.5 total knee arthroplasties per year per 10,000 individuals in that age group (3). Therefore, approximately 322,000 TKAs were performed in 2010 for those aged 45 to 64. A 2010 study from The Centers for Disease Control and Prevention found the average cost of home health care following TKA to be \$3,709 per episode of care per patient (5). This results in nearly \$1.2 billion dollars in U.S. healthcare spending in 2010 for home care following TKA for those aged 45 to 64. The reason for the high cost of home health care may be the state regulations governing home health care agencies. The Louisiana Department of Health and Hospitals states that 'skilled home health care,' found under the definition of 'home health agency' in the official Louisiana Home Health State Regulations, is to include skilled nursing and at least one of the following services: physical therapy, occupational therapy, speech therapy, medical social services, or home health aide services (9). These regulations place pressure, whether conscious or subconscious, on the home health agency to over utilize skilled nursing services for those patients aged 45 to 64 recovering from TKA. Skilled nursing home health care services for this particular patient population usually involves managing the patient's medications and providing wound care services. A cohort study by Bleijenberg et al published in the Journal of the American Geriatric Society in 2017 found that only 10.3% of adults aged 65 to 69, which is above the age cutoff for this prospective study, had difficulty with managing their medications (10). Also, in the author's clinical experience, it is rare for an orthopedic surgeon to allow any other clinician to manage post-operative dressing changes except those clinicians under the surgeon's direct supervision; though further research in this area would be helpful. Furthermore, utilization of TKA, and the home care cost associated with recovery from TKA, is on the rise. As of 2009, the number of primary TKAs performed annually in the U.S. among all age groups exceeded 620,000 procedures, which is more than doubled when compared to the previous decade (7). Smartphones and other technologies may provide a solution to the rising costs of home health care following TKA for those aged

45 to 64. Over the past decade, the smartphone has become an integral part of most people's lives. The latest Pew Research Data from February 2018 shows that 73% of individuals aged 50 to 64 own a smartphone (8). Smartphones would allow the patient to have direct multimedia access to a prescriptive exercise program designed by a licensed Physical Therapist without an in-person home visit, as well as to have communication directly with their Physical Therapist through secure in-app messaging or e-mail. The patient would benefit by having reduced intrusion in their home environment, convenient access to their Physical Therapist and their Physical Therapist's plan of care, and financial savings due to the elimination of home health care services following TKA. The Physical Therapist would benefit from the ability to quickly interact with the patient to mitigate any adverse events and to efficiently assist a greater number of patients compared to traditional home-based physical therapy. Third-party payors would benefit from drastically reduced home care costs for those recovering from TKA.

Objectives

The primary objective will be to determine the efficacy of the app for those recovering from TKA compared to traditional home care during the home bound portion of the patient's recovery from TKA by comparing ROM improvement outcomes between the intervention group and the control, as well as measuring the subjective improvement in functional outcomes for the intervention group by using the Short MAC. A secondary objective of the study is to determine the relationship between the intervention participants' self-reported frequency of engagement with the app and their qualitative and quantitative outcomes, otherwise known as the dose-response.

Methods

The intervention group for this study are those who will utilize the smartphone app to complete the home-based portion of physical therapy following TKA. The control group are those who have completed traditional home health physical therapy following TKA. Inclusion criteria for the study consists of participants aged 45 to 64, the participant will have undergone unilateral TKA, and the participant should be discharged directly to home from the hospital. Participant's data from the intervention group will be excluded from the study if they do not engage with the app within 24 hours of discharge from the hospital, if the participant neglects to engage with the app over any 24-hour period during the study, or if the participant is readmitted to the hospital at any point during the home bound portion of their recovery.

Subjective outcomes for the participants in the intervention group will be assessed by the Short MAC and objective outcomes will be assessed by measuring total knee ROM improvement. The intervention participants' self-reported frequency of app usage will be compared to the participants' outcomes to determine the dose-response of the app. The Short MAC has been previously shown to be a reliable, valid, and responsive indicator of qualitative improvement in a patient's functional status post-TKA and total hip arthroplasty (THA) by Whitehouse et al (1). Minimum important change for Short MAC has been found to be 7.9 points for small change, 8.4 points for medium change, and 12.1 points for large change (2). The total knee ROM

improvement in the treatment group will be compared against a control group of patients who have completed traditional home care from a variety of physical therapists following TKA.

The primary hypothesis is that the intervention group will show a statistically equal outcome to the control group, demonstrating the efficacy of a low-cost alternative to traditional home care. The null hypothesis is that the research group will not show a statistically equal outcome to the control group. The first alternative hypothesis is that the intervention group will show a statistically significant improvement over the control group. The second alternative hypothesis is that the control group will show a statistically significant improvement over the intervention group.

Data for the control group will be taken from approximately 30 individuals aged 45 to 64 that have previously completed traditional home health physical therapy care from a variety of physical therapists following TKA. Data for the intervention group will be taken within 48 hours of being discharged from the hospital from approximately 30 participants who agree to use the smartphone app to complete the home-based physical therapy portion of their recovery from TKA. Intervention group participants will complete an introductory meeting with the physical therapist in-person to onboard the patient to the app and perform the initial data collection. Participants in the intervention group will be encouraged to engage with the app 3 to 5 times per day as able. The intervention participant will have the ability to communicate any questions or concerns to the Physical Therapist via e-mail or phone call throughout the homebound portion of their recovery. For safety monitoring, a physical therapist will contact the intervention group participant via phone or e-mail every 24 to 48 hours to ensure no adverse events have occurred. A final in-person meeting will occur between the Physical Therapist and the participant at the conclusion of the homebound portion of the participants' recovery for the purpose of final data collection. A two-tailed t-test for two independent groups will be used to compare the means for total ROM improvement between the intervention group and the control group. Data from the Short MAC will be used to describe the overall subjective effect of the intervention on the patient's functional abilities. The relationship between the Participants self-reported frequency of app usage and their combined subjective and objective outcomes will be used to understand the dose-response of the app. Information about dose-response will be integral in establishing guidelines regarding frequency of app usage for optimal results.

Conclusion

Traditional home health care for individuals recovering from unilateral TKA is expensive and provides a higher level of service than most individuals, aged 45 to 64, require. Use of smartphone technology has the potential to drive down costs while maintaining outcomes for this patient population. The proposed randomized controlled trial would determine the efficacy and proper dose-response of a smartphone app to reduce costs and maintain outcomes for the desired patient population compared to traditional home care.

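### Controls are selected on having completed home care and app participants by different rules applied after treatment starts, so neither mean is the result of being given that care

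*Protocol*

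**What the plan says.** The Methods section defines the control group three times, each time by completion:

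- In the group definitions: "The control group are those who have completed traditional home health physical therapy following TKA".
- Where the ROM comparison is described, the comparator is "a control group of patients who have completed traditional home care from a variety of physical therapists following TKA".
- Where the data sources are given, the source of control data is "approximately 30 individuals aged 45 to 64 that have previously completed traditional home health physical therapy care from a variety of physical therapists following TKA".

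Nothing in the protocol admits people who began home care and stopped, or says how they are handled.

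The app group is "approximately 30 participants who agree to use the smartphone app to complete the home-based physical therapy portion of their recovery from TKA", with initial data taken within 48 hours of hospital discharge. Methods then removes app participants' data in three situations: no engagement within 24 hours of discharge, hospital readmission during the homebound period, and "if the participant neglects to engage with the app over any 24-hour period during the study".

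The Objectives section sets out to "determine the efficacy of the app for those recovering from TKA compared to traditional home care during the home bound portion" of recovery. The planned analysis is stated as "A two-tailed t-test for two independent groups will be used to compare the means for total ROM improvement" between the groups.

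**The concern.** Completing a course of care happens after treatment starts and may itself depend on how recovery is going. Selecting controls on it leaves out patients who declined further visits, stopped for pain or a complication, moved to another setting, or finished early because they did well. The control mean then describes completed home care, whereas the objective asks about home care as given.

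The app group is also filtered after entry, but by engagement and readmission. The rules differ, so there is no reason to expect the two selections to cancel. A difference in mean ROM gain, or the lack of one, could reflect who was kept in each group.

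The main hypothesis is that outcomes are equal, and the protocol states no margin. It therefore gives no basis for calling a bias of a few degrees tolerable. Nor can analysis repair this later: if records are gathered only for completers, the early stoppers are not in the data.

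**Working it through.** **Plan's own figures.** The protocol gives about 30 per group. It gives no alpha, power, standard deviation (SD), margin, early-stop rate or outcomes of stoppers, so there is no figure to reproduce. Everything below is illustration on stated assumptions.

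**Step 1: effect of the control rule.** Let C be the completers' mean ROM gain, p the share of home-care starters who stop early, and d the amount by which their mean gain falls below C.

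Mean of all starters = (1 − p)·C + p·(C − d) = C − p·d, so the completers' mean overstates it by p·d.

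- Assumed p = 10%, d = 10 degrees: 0.10 × 10 = 1 degree.
- Assumed p = 20%, d = 20 degrees: 0.20 × 20 = 4 degrees.
- If stoppers left because they recovered early, d is negative and the control mean is understated.

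In SD units, with 5% to 30% stopping and a gap of 0.25 to 1.0 SD, the shift runs from 0.05 × 0.25 = 0.0125 SD to 0.30 × 1.0 = 0.30 SD. A middle case is 0.20 × 0.5 = 0.10 SD.

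**Step 2: both rules together.** Let q be the share of app starters whose data are dropped, and e the amount by which their mean gain falls below that of those kept. Then:

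expected observed difference (app − control) = difference among all starters + q·e − p·d.

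If q·e also lay between 1 and 4 degrees (again assumed), the net bias would lie between 1 − 4 = −3 and 4 − 1 = +3 degrees. The protocol fixes neither term, so the sign of the net bias is undetermined.

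**Step 3: changing one rule only.** If early stoppers are added to the controls while app data are still dropped, the p·d term goes and q·e stays. On the same assumption that those dropped do worse, the comparison then favours the app by 1 to 4 degrees.

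**Step 4: scale against the planned test.** With 30 per group and an assumed two-sided alpha of 0.05:

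- Standard error of the difference = SD × √(2/30) = 0.258 SD.
- Difference detectable with 80% power = (1.96 + 0.84) × 0.258 SD ≈ 0.72 SD.
- A 4-degree observed difference reaches significance only if the SD is below 4 / (2.00 × 0.258) ≈ 7.7 degrees.
- With no true difference, a bias of 0.10 SD is 0.10/0.258 ≈ 0.4 standard errors, and the test rejects about 7% of the time. A bias of 0.30 SD is about 1.2 standard errors, and it rejects about 21% of the time (normal approximation).

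The low end of the range is negligible; the high end is not.

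**The case against.** **The app group is selected too.** It is not analysed as all starters, because Methods removes late starters, anyone with a gap in use, and readmitted patients. This stands. The defect is two unlike post-treatment selections, not a bias in the control group alone.

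**Completion may be over-read.** The protocol sets no completion criterion, such as visits made or goals met. The past tense might mean only that the controls' care lies in the past. That reading is possible, but the word appears in all three definitions and nothing admits early stoppers. Someone selecting records from this text would have no ground to include them.

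**It follows from the design label.** Study Design and Conclusion call the trial randomized, yet controls are people already treated. That is a related but separate contradiction. A concurrent or even randomized control arm cut down to completers would carry the same bias.

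**Stronger readings.** A reader might infer that the control benchmark is set too high, so that the app could be judged inferior for that reason alone. The documents do not support this: early stoppers may have done better or worse, and the 1 to 4 degrees rests wholly on assumed inputs. Even 4 degrees alone would be significant only with an SD below about 7.7 degrees. A reader might also infer that the two selections act in opposite directions. That holds only if those left out of each group did worse, which the protocol does not show.

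**The remedy can mislead.** Changing only the control rule could tilt the comparison towards the app, as Step 3 shows. This stands, and the fix below changes both rules together.

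**Conclusion.** The concern holds in limited form. Control membership depends on completing home care, app membership on entry followed by engagement and readmission filters, and the two means are not comparable as results of being given each kind of care. The text alone establishes this, on the natural reading that people who stopped early do not count as having completed care.

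Neither direction nor size can be established. The illustrative shift in the control mean is 1 to 4 degrees (10% to 20% stopping, gain 10 to 20 degrees lower), or 0.0125 to 0.30 SD on the wider assumed range, with the sign reversed if stoppers recovered early. The app-group filter adds a further term of unknown size. The plan should be changed because the choice of whom to compare is fixed in this protocol and cannot be undone in analysis; no particular wrong conclusion has been shown to follow.

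**What to change.** Make these changes together:

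1. Define controls at the start of care: consecutive eligible patients (age 45 to 64, unilateral TKA, discharged directly home) who started home health physical therapy in a stated calendar period, whether or not they completed it.
2. Keep all app starters in the primary ROM comparison, so that late start, gaps in use and readmission no longer remove data from it.
3. In both arms, use the last recorded ROM with its date, and take time since discharge into account in the comparison, because early stoppers will have been measured sooner.
4. Report by arm how many stopped early and why. The comparison of home-care completers with app adherers may be kept as a sensitivity analysis.

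The cost is a changed selection rule and some extra records to review. The main drawback is that early stoppers will have an earlier last ROM, or none. The protocol does not say whether ROM was recorded during home care for controls, so check this before the rule is fixed. The change reduces this selection bias but does not make the comparison randomized.

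### Agreement to use the app selects the app group only, and the inclusion criteria contain no access or willingness condition common to both groups

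*Protocol*

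**What the plan says.** The inclusion criteria are in the Methods section of the protocol and begin with age: "Inclusion criteria for the study consists of participants aged 45 to 64". Two further conditions follow, a TKA on one side only and going straight home after the hospital stay. The list ends there.

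Further on in Methods, the two groups are described by their sources. The app group is "approximately 30 participants who agree to use the smartphone app". The control group is "approximately 30 individuals aged 45 to 64 that have previously completed traditional home health physical therapy care". Agreement is a condition of entry to the first group and has no counterpart in the second.

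The Background reports that "73% of individuals aged 50 to 64 own a smartphone". The protocol does not say that a participant must own a phone, nor whether phones would be supplied.

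Methods also sets a rule for the app group alone: "Participant's data from the intervention group will be excluded from the study if they do not engage with the app within 24 hours of discharge". Controls have no corresponding rule.

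The two groups are compared on mean total ROM improvement by a two-tailed, two-sample t-test, with no matching or adjustment described. The primary hypothesis is that outcomes are statistically equal. The Study Design and Conclusion sections call the study randomized, but no allocation step is described.

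**The concern.** A comparison of two group means estimates the effect of treatment only if the groups would have had the same mean under the same treatment. Here one group consists of people who accepted app-based therapy, and the other of people who finished conventional home care and were never asked about an app. If people able and willing to use an app recover ROM differently from those who are not, that difference goes straight into the treatment contrast.

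The claim at risk is the protocol's main one, that the app does as well as home care. A selection difference favouring the app group could hide a real deficit, and one in the other direction could create a false deficit. With an unadjusted t-test, the result gives no means of telling these apart from a true treatment effect.

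**Working it through.** The protocol states no SD, power, significance level or equivalence margin, so there is no figure of its own to reproduce. The check has two parts.

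**1. Selection conditions side by side (Methods)**

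| Condition | App group | Control group |
|---|---|---|
| Age 45 to 64 | yes | yes |
| Unilateral TKA, discharged directly home | yes | general criterion, applies to both |
| Agreed to use the app | yes, explicit | not asked |
| Access to a smartphone | inferred from app use | not asked |
| Already completed home care | no | yes, explicit |
| Removed for not engaging within 24 hours | yes | no such rule |

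Each group passes a filter that the other does not. The difference in selection rules is plain on the text. A difference in prognosis is to be expected but is not shown.

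**2. Illustration of size**

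Inputs from the protocol: about 30 per group, and 73% smartphone ownership (ages 50 to 64, used as a proxy for 45 to 64). Assumed: controls own phones at that rate, everyone in the app group has access, and the gap in mean ROM gain between people without and with a phone is 3, 5 or 10 degrees.

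- Expected controls without a smartphone: 30 × (1 − 0.73) = 8.1. The 2.5% and 97.5% points of a binomial(30, 0.27) are 4 and 13. The probability of at least 5 is 0.94.
- Control mean = 0.73 × (owners' mean) + 0.27 × (non-owners' mean), so the shift relative to owners only is 0.27 × gap:
  - gap 3: 0.27 × 3 = 0.81 degrees
  - gap 5: 0.27 × 5 = 1.35 degrees
  - gap 10: 0.27 × 10 = 2.7 degrees

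Willingness, the explicit part of the filter, has no figure in the protocol. If 80% of owners would agree (assumed), the share able and willing is 0.73 × 0.80 = 0.584. Then 30 × (1 − 0.584) = 12.5 controls could not or would not have used the app.

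On the SD scale, the bias is the share unable or unwilling times an assumed gap in SD, and SE = √(2/30) = 0.258 SD. By normal approximation, the chance of a significant t-test when the app has no effect, at an assumed two-sided 5%, is:

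| Assumed gap | Ownership only (share 0.27): bias, rate | With 80% willingness (share 0.416): bias, rate |
|---|---|---|
| 0.2 SD | 0.05 SD, 5.5% | 0.08 SD, 6.2% |
| 0.5 SD | 0.14 SD, 8.2% | 0.21 SD, 12.7% |
| 0.8 SD | 0.22 SD, 13.3% | 0.33 SD, 25.2% |

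The effect runs from negligible to material, depending entirely on gaps and a willingness rate that the protocol does not supply.

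**The case against.** The strongest reply is that this is a symptom. Controls who have already finished care cannot have been randomized with the app group, and that is the root defect. Under concurrent randomization after consent, access and willingness would balance between the allocated groups without being listed as criteria. This stands, and it limits the point: a common criterion removes one source of bias and leaves the rest of a historical comparison in place.

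A reader might infer that the imbalance would persist under true randomization simply because the criterion is missing. The documents do not support that. What would persist comes from the 24-hour exclusion, which applies to the app group only: a participant without access would be dropped there, while the same person would be kept as a control. That is a separate rule, and a criterion on access would blunt it only in part.

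Three other stronger readings also fail:

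- That app participants must own a phone. This is inferred; only agreement to use the app is stated.
- That controls are unselected. They are selected on having completed home care, which could itself favour particular patients.
- That the groups are shown to differ in motivation, social position or health. No passage shows this.

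It is also fair to object that the 0.8 to 2.7 degree shifts rest on assumed gaps and that, with no SD or margin in the protocol, they cannot be called large or small. That is why they serve only as illustration.

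**Conclusion.** The point holds as a design weakness. The selection rules differ between the groups: agreement to use the app is required on one side only, and the inclusion criteria contain nothing that would equalize access or willingness. Followed as written, the plan compares differently selected groups with an unadjusted test and uses the result to support a claim of equal outcomes.

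The bias itself is not established in size or direction. The illustrative figures (about 8 of 30 controls without a phone, a shift of roughly 0.8 to 2.7 degrees) rest on a general ownership rate for a slightly different age range, on an inferred need for a phone, and on assumed ROM gaps. With a small gap and ownership alone, the t-test would be nearly unaffected (5.5% against an assumed 5%). Confidence is high on the difference in rules and moderate at most on its practical importance.

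**What to change.** First reconcile the randomized label in Study Design and Conclusion with the group definitions in Methods. Then take one of two routes.

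**If the study is randomized:** add as an inclusion criterion for all participants that the person has access to a smartphone and agrees to use the app if allocated to it, assessed before allocation. This also keeps lack of access from triggering the 24-hour exclusion in the app group. It does not deal with later non-engagement, which needs its own correction. The cost is one line in the criteria and one screening question.

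**If controls remain past patients:** restrict them to those with documented smartphone access where records allow, state that willingness cannot be established in retrospect and so cannot be matched, and do not claim equal outcomes from the comparison. The cost is a records check and a smaller control pool, possibly about a quarter fewer eligible controls at 73% ownership, so more records may be needed to reach about 30.

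Either route narrows the control population towards the people for whom the app is intended. Neither removes the other biases of a historical control.

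### The 24-hour app-engagement exclusion runs from hospital discharge, but onboarding may take place up to 48 hours after discharge, so study scheduling alone can remove a participant from the app arm

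*Protocol*

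**What the plan says.** All the relevant text is in the Methods section of the protocol.

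- **Exclusion rule.** The paragraph on eligibility states: "Participant's data from the intervention group will be excluded from the study" in any of three circumstances. Two concern use of the app. The first is "if they do not engage with the app within 24 hours of discharge from the hospital"; the second is "if the participant neglects to engage with the app over any 24-hour period during the study". The third is hospital readmission. These exclusions are written for the app group only.
- **Timing of the initial data.** The later paragraph on data collection states: "Data for the intervention group will be taken within 48 hours of being discharged from the hospital".
- **What happens at that meeting.** The next sentence gives each app participant "an introductory meeting with the physical therapist in-person to onboard the patient to the app and perform the initial data collection". Final data come from a separate in-person meeting at the end of the homebound period.
- **Group sizes.** The app group is "approximately 30 participants who agree to use the smartphone app". For the controls, "Data for the control group will be taken from approximately 30 individuals aged 45 to 64" who have already completed home care. No engagement condition applies to them.

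**The concern.** The deadline for first use of the app and the deadline for being introduced to it are both counted from discharge, and the first falls 24 hours before the second. A person whose introductory meeting takes place at hour 30 may start using the app at once and still meet the definition of someone who failed to engage.

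The rule appears meant to identify participants who did not use the app. As written, it can also pick out participants whom the therapist met later. Any such loss falls on one arm only and depends on logistics. It would reduce precision unless those removed are replaced. It would also bias the comparison of ROM improvement if people met later recover differently. The protocol gives no information on whether they do, or in which direction.

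This is a separate matter from whether non-engagers should be dropped at all. If the sponsor keeps an engagement rule, or moves it to a sensitivity analysis, the start of the clock still has to be right.

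**Working it through.** **Step 1: which data the 48-hour window covers.** The protocol describes two in-person data collections for the app group: one at the introductory meeting and one at the end of the homebound period. Only the first can sensibly carry a limit of 48 hours from discharge. That meeting is also where onboarding takes place, so onboarding may occur as late as hour 48.

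**Step 2: the windows side by side, both counted from discharge.**

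| Event | Latest permitted time |
|---|---|
| First engagement with the app, to avoid exclusion | 24 h |
| Introductory meeting (onboarding and initial data) | 48 h |

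Overhang: 48 − 24 = 24 h. During those 24 hours a meeting is on time under the data-collection paragraph, but the exclusion has already been triggered. The protocol does not require onboarding before discharge or by hour 24, does not start the clock at onboarding, and makes no exception for later onboarding.

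**Step 3: the second engagement clause.** It covers any 24-hour period during the study, but the protocol does not say when the study starts for a participant. If it starts at discharge, someone onboarded at hour 40 has already gone 24 hours without engagement and is excluded by this clause too. If it starts at onboarding, the problem does not arise here.

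**Step 4: illustration of size.** The protocol gives no distribution of onboarding times and no figure to reproduce. Inputs: 30 per group (the protocol's approximate figure), an assumed share f of app participants onboarded after hour 24, no replacement, no other exclusions and equal variances.

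Remaining app participants: n = 30 × (1 − f).

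Standard error relative to 30 per group: √[(1/n + 1/30) / (2/30)].

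| f (assumed) | n | Ratio inside the root | Relative standard error |
|---|---|---|---|
| 10% | 27 | (0.03704 + 0.03333) / 0.06667 = 1.056 | 1.03 |
| 25% | 22.5 | (0.04444 + 0.03333) / 0.06667 = 1.167 | 1.08 |
| 50% | 15 | (0.06667 + 0.03333) / 0.06667 = 1.500 | 1.22 |

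The 22.5 is an expected count. The 50% row is what uniform timing over 0 to 48 hours would give; nothing in the protocol says timing is uniform.

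**The case against.** **The two rules can both be met.** A meeting in the first 24 hours satisfies both, and the protocol does not clearly rule out a meeting in hospital or on the day of discharge. The exclusion rule may simply presuppose early onboarding. This stands as a limit on the point. A reader might infer that the passages flatly contradict each other, or that compliant participants will be lost. The text supports neither: it permits a conflict without making one inevitable. But a rule that removes data should not depend on a scheduling practice that is not written down.

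**The 48 hours attach to data, not to onboarding.** That is literally so, but the next sentence puts both in the same meeting.

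**A participant might use the app before onboarding.** The protocol does not exclude this expressly. It describes no such route, however, and gives onboarding as a purpose of the meeting. The point does rest on this reading.

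**The issue disappears if everyone is analysed regardless of engagement.** For the main comparison that is true. It would remain in any adherence-based set.

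**The size is hypothetical.** This also stands. The shares are assumed, a therapist aware of the 24-hour rule would probably schedule around it, and approximately 30 may mean 30 with usable data. In that last case those removed are replaced and the loss of precision disappears, though the selection does not.

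**Conclusion.** The point holds in a limited form. The windows are compatible only when onboarding happens within 24 hours of discharge, which the protocol does not require. A participant onboarded between hours 24 and 48 complies with the visit window and can still be removed from the app arm through scheduling rather than behaviour. The second engagement clause has the same effect if the study is counted from discharge. This rests on two readings: that the 48-hour limit applies to the introductory meeting, and that the app is not used before it.

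The number affected is unknown. The increases in standard error of 3%, 8% and 22% show what the assumed shares would mean without replacement; they are not estimates for this trial. A reader might take the 50% row as a forecast that half the arm would be lost, or conclude that the comparison is biased. The documents support neither, since they give no onboarding times and nothing on how those met later recover. The case for a correction rests on the mismatch in the text, and the remedy is cheap.

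**What to change.** Reconcile the two paragraphs of Methods so that no participant's data can be excluded because of the time at which the study itself held the onboarding meeting. One way is to start the clock for both engagement-based data-exclusion clauses at that meeting and leave the visit window as it is. Changing only the first clause is not enough, because the second could still remove the same people. Another way is to state an onboarding window that ends early enough for the present clock to be met. The protocol gives no basis for preferring one over the other, so the choice is the sponsor's.

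Whichever is chosen, use the same start point in any adherence-based sensitivity set, and record the time of onboarding so that the rule can be applied.

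Moving the clock is a change to the wording of the exclusion sentence, with no added visits, staff or patients. A tighter onboarding window would constrain scheduling instead.
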